4. STUDY PROCEDURES

4.1. Standard of Care Arm

3.4.1.1 Provision of Services

Facilities in the standard of care arm will provide routine services. No intervention activities will be conducted. Standard of care procedures involve counseling HIV-positive individuals about the importance of partner testing and providing ‘referral slips’ to the index client to distribute to sex partners. Partner testing will follow Ministry of Health National Guidelines using serial testing with Determine and Uni-Gold. Those that test positive will be counseled and referred to ART services following routine care.

3.4.1.2 Baseline Visit for Index Client

A random sample of individuals will be screened and consented as they exit their ART visit. This will include ART clients who report having a sexual partner with an unknown HIV status. After written informed consent has been obtained, study staff will collect basic socio-demographics (including age, gender, marital status, and number of partners), HIV characteristics (date of HIV diagnosis, whether on ART and date started), and the number of eligible sexual partners who qualify for index testing referral slips. Individuals will also be asked whether they were offered a referral slip on the day of the survey.

Follow-up Visit of Index Clients

All index clients will be seen by study staff when they come for their next ART follow-up visit. A brief survey will be performed to collect information about whether the client disclosed their HIV status to their sex partner(s), whether they gave referral slips to their partner(s), and knowledge about whether partners completed a test, knowledge of their partner's test result, and knowledge about their partner's linkage to care. We will also survey the index client to determine whether any gender-based violence or fear of gender-based violence resulted from use of the self-tests. Index clients who do not return for their ART follow-up visit (more than two weeks late) will be traced through standard site protocols and surveyed either in the community or at the facility, if they return to care.

HIV testing registers will also be reviewed to measure the number of individuals tested through partner referrals and the proportion of partner referral tests who were identified as HIV-positive. All registry data will be anonymized. Records from partner notification clients aged 15 years and older will be included in the study. For those who are HIV-positive, the HTC and ART registers will be reviewed to determine if the patient started ART and presented for their four-week follow-up visit.

4.2. Optimized Standard of Care Arm

4.2.1. Partner Notification and Referral

The study team will provide trainings, job aids, and regular mentorship to promote optimized standard of care in regards to partner notification and referral strategies for HIV-positive clients with partners who have an unknown HIV status. Under optimized standard of care, providers will ask clients at every ART visit whether they have current or recent (within 12 months) sex partners with unknown HIV status or tested negative for HIV more than 6 months ago. Clients will be counseled on the importance of partner notification and testing and given a partner notification slip to assist in partner notification and testing referral. Individuals will be counseled to ask their partners to return the referral slips when they come for testing. Partners who present at the facility for HIV testing will be tested in private rooms by trained HDAs following Ministry of Health guidelines. HDAs will ask all clients presenting for testing whether they were referred by a partner and this will be indicated in a column in the HIV testing register. Serial HIV testing will be performed with Determine and Uni-Gold as per standard of care. Those that test positive will be counseled and referred to ART services. ART initiation will follow standard clinic protocols under the universal treatment (Test and Treat policy).

3.4.2.2 Baseline Visit for Index Client

A random sample of individuals will be screened and consented as they exit their ART visit. This will include ART clients who report having a sexual partner with an unknown HIV status. After written informed consent has been obtained, study staff will collect basic socio-demographics (including age, gender, marital status, and number of partners), HIV characteristics (date of HIV diagnosis, whether on ART and date started), and the number of eligible sexual partners who qualify for index testing referral slips. Individuals who consent will also be asked whether they were offered a referral slip on the day of the survey.

Follow-up Visit of Index Clients

All index clients will be seen by study staff when they come for their next ART follow-up visit. A brief survey will be performed to collect information about whether the client disclosed their HIV status to their sex partner(s), whether they gave referral slips to their partner(s), and knowledge about whether partners completed a test, knowledge of their partner's test result, and knowledge about their partner's linkage to care. We will also survey the index client to determine whether any gender-based violence or fear of gender-based violence resulted from use of the self-tests. Index clients who do not return for their ART follow-up visit (more than two weeks late) will be traced through standard site protocols and surveyed either in the community or at the facility, if they return to care.

HIV testing registers will also be reviewed to measure the number of individuals tested through partner referrals and the proportion of partner referral tests who were identified as HIV-positive. All registry data will be anonymized. Records from partner notification clients aged 15 years and older will be included in the study. For those who are HIV-positive, the ART register will be reviewed to determine if the patient started ART and presented for their four-week follow-up visit.

At the time of follow-up, a random sample of 40 index clients (20 men and 20 women) will be selected and asked to participate in semi-structured, in-depth interviews to explore the feasibility and acceptability of providing referral slips to partners, including challenges with disclosure and questions around harm or perceived risk of harm due to distributing the referral slip.

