3. HYPOTHESES

- Aim 1: Group self-testing will (1) increase the number of OPD and STI clients tested for HIV, (2) increase HIV testing yield, and (3) be cost-effective compared to the optimized standard of care
- Aim 2: Self-test kits given to index clients will (1) increase the number of index partners who test for HIV; (2) increase yield of partner testing, and (3) be cost-effective compared to the optimized standard of care for partner notification and testing, and will (4) increase partner disclosure by the index client

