3. AIM 2: PARTNER SELF-TESTING

3.1. OBJECTIVES

3.1.1. Primary Objectives:

- To determine whether providing index clients with HIV self-test kits for partners results in a greater number of partners tested as compared to optimized standard of care for partner notification and testing (referral slip)
- To determine whether providing index partners with HIV self-test kits is cost-effective compared to optimized standard of care using referral slips

3.1.2. Secondary Objectives:

- To assess the acceptability of giving self-test kits to index clients for partner testing
- To determine whether providing index partners with HIV self-test kits is superior to optimized standard of care in regard to identifying HIV+ partners (yield of testing)
- To determine whether providing index partners with HIV self-test kits is superior to optimized standard of care in regard to linkage rates among those who identify as HIV-positive
- To determine whether providing self-test kits to index clients and their partner is superior to optimized standard of care in regard to partner disclosure by the index client

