4.3. Partner Self-Testing Arm

3.4.4.1 Baseline Visit for Index Client

A random sample of individuals will be screened and consented as they exit their ART visit. This will include ART clients who report having a sexual partner with an unknown HIV status. After written informed consent has been obtained, study staff will collect basic socio-demographics (including age, gender, marital status, and number of partners), HIV characteristics (date of HIV diagnosis, whether on ART and date started), and the number of eligible sexual partners they plan to give self-test kits.

The study staff will counsel the index client on how to administer an HIV self-test and will provide one self-test kit for each sexual partner within the last 12 months with unknown status (or HIV-negative more than 6 months ago) who lives within the catchment area of the facility and for whom the index client is willing to provide the test kit (up to three sexual partners). Index clients will also be given self-test kits for themselves if they wish to use them to complete couples counseling. All HIV self-test kits will be labeled with a unique ID linked to the index client participant. The ID will also be used to link index client survey responses with returned self-test kits.

The number of partners and the number of kits provided will be documented by study staff. Each self-test kit will be in a package that also contains a referral card. The referral card can be used for (1) those who test HIV-positive and need to present for confirmatory testing and link to care, (2) those who do not want to use the self-test kit and would rather test with an HDA, or (3) clients who experience difficulty or discomfort with the self-test kit and choose to test at a facility. The referral card will include information about the fa-

cility, including a map. The card will also contain a notation that if it is returned to another facility, the facility should contact the study team so that the card can be collected and recorded as “returned”. Study staff will periodically visit nearby testing sites to determine if any referral cards have been returned to those sites.

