3.4.4.4 Follow-up Visit of Index Clients

All index clients will be seen by study staff when they come for their next ART follow-up visit. A brief survey will be performed to collect information about whether the client disclosed their HIV status to their sex partner(s), whether they gave self-test kits to their partner(s), and knowledge about whether partners completed the test, knowledge of their partner’s test result, and knowledge about their partner’s linkage to care. We will also survey the index client to determine whether they were able to successfully show their partner(s) how to use the kit and whether any gender-based violence or fear of gender-based violence resulted from use of the self-tests. Index clients who do not return for their ART follow-up visit (more than two weeks late) will be traced through standard site protocols and surveyed either in the community or at the facility, if they return to care.

A random sample of 40 index clients (20 men and 20 women) and 40 index partners (20 men and 20 women) will be selected and asked to participate in semi-structured, in-depth interviews to explore the feasibility and acceptability of providing self-test kits to partners, including challenges with disclosure and questions around harm or perceived risk of harm due to distributing the kits.

2.4.4.5 *Follow-up Visits with Index Partners*

Index partners will be recruited for in-depth interviews through index clients (n=40). During follow-up visits with index clients, a random subset of clients will be given a study invitation card to be given to their sexual partner who was given a self-test kit. The study invitation card will describe the in-depth interview they are being recruited for and provide a study-specific phone number the index partner can call in order to participate in the study. In addition, index clients will be asked if the study team could call the randomly selected partner to discuss the study. Index clients will be told the purpose of the call. If index clients give permission to contact the index partner, up to 2 phone numbers will be collected. Index partners will be called up to 3 times over a 2-week period for recruitment into the study. If the index partner cannot be reached after the third try, the partner will be listed as “unreachable” and excluded from the study.

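### Aim 2 does not record disclosure at baseline and gives its follow-up question no reference period, so earlier disclosure dilutes any effect of the kits and can bias the arm comparison unseen

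*Combined protocol and SAP*

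**What the plan says.** **Objective.** Section 3.1.2 and the schema make it a secondary objective to show that the kits are "superior to optimized standard of care in regard to partner disclosure by the index client". Section 3 (Hypotheses) expects them to "increase partner disclosure by the index client".

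**Baseline.** Each arm has an itemised list.
- Standard of care (3.4.1.2): socio-demographics, HIV characteristics, number of eligible partners, and one further item: "Individuals will also be asked whether they were offered a referral slip on the day of the survey".
- Optimized standard of care (3.4.2.2): the same, including "the number of eligible sexual partners who qualify for index testing referral slips".
- Self-testing (3.4.4.1): socio-demographics, "HIV characteristics (date of HIV diagnosis, whether on ART and date started"), "and the number of eligible sexual partners they plan to give self-test kits".

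None of the three lists mentions disclosure.

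**Follow-up.** All three arms are surveyed at the next ART visit. The two comparator arms use the sentence "A brief survey will be performed to collect information about whether the client disclosed their HIV status to their sex partner(s"). The self-testing arm (3.4.4.4) asks "whether the client disclosed their HIV status to their sex partner(s), whether they gave self-test kits to their partner(s"). Neither text states a time window.

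**Eligibility.** Sections 3.2.1 and 3.2.2 turn on whether and when the partner was tested, not on what the partner knows about the client.

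**Analysis.** Section 3.5.1.1 names partner testing and partner positivity as outcomes. Disclosure is not named, and no rate or power is given for it.

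**The concern.** The hypothesis is about disclosure that follows the kit or slip. Participants are recruited at ART visits, and some may have disclosed long before. A partner who has never tested, or who last tested negative more than six months ago, counts as having unknown status even if that partner already knows the client is HIV-positive. Such pairs enter the study with the event already behind them.

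Two things are at stake. A real effect may look small and be missed. And if the arms enrol clients with different disclosure histories, that difference enters the result with no recorded variable to reveal it or adjust for it.

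**Working it through.** The plan has no disclosure figure to reproduce. Its only Aim 2 power figure tied to stated rates (89%, 20% vs 40%) concerns partner testing. The stated inputs give more than 99.9% for it, which is a separate matter.

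**Inputs from section 3.5.1.1:** 600 index clients per arm, 5 facilities per arm (120 each), ICC 0.004. Design effect = 1 + 119 × 0.004 = 1.476.

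**Assumptions (not in the documents):** *d* = share already disclosed at enrolment; *i* = share of the rest who disclose by follow-up.

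**1. Dilution.** Ever disclosed at follow-up = *d* + (1 − *d*)*i*. With *d* = 60% in both arms:
- Optimized care: 0.60 + 0.40 × 0.30 = 72%
- Self-testing: 0.60 + 0.40 × 0.50 = 80%

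The difference is 8 points, against 20 among those not yet disclosed. With equal *d*, the difference is always (1 − *d*) times the true one.

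**2. Power.** Illustration with *i* = 20% vs 40%, a cluster-level t-test with 8 df and ICC 0.004:

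| Prior disclosure, both arms | Difference, ever disclosed | Power, ever disclosed | Power, only those undisclosed at baseline (difference 20 points) |
|---|---|---|---|
| 20% | 16 points | 98% | 99.9% |
| 50% | 10 points | 75% | 99% |
| 70% | 6 points | 46% | 93% |
| 80% | 4 points | 31% | 83% |

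The last column already allows for the smaller denominator.

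**3. No true effect.** With equal *i*, the difference at follow-up is (*d*₂ − *d*₁)(1 − *i*). Simulation used 4,000 trials with 5 facilities of 120 per arm, ICC 0.004, *i* = 20% in both arms and a t-test on facility proportions:

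| Prior disclosure | Estimated difference | Rejections at 5% |
|---|---|---|
| 50% vs 50% | 0.0 points | 5.0% |
| 50% vs 55% | 4 points | 17% |
| 50% vs 60% | 8 points | 55% |

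**4. Imbalance by chance alone.** SE of the arm difference in prior disclosure = √(2*d*(1 − *d*) × design effect / 600). At *d* = 50% and ICC 0.004: √(0.5 × 1.476 / 600) = 3.5 points, so 1.96 SE is 6.9 points. At an assumed ICC of 0.05 the design effect is 6.95, the SE 7.6 points and 1.96 SE 14.9 points.

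**5. If the form already asks about the time since enrolment.** The numerator becomes (1 − *d*)*i*, but clients who had already disclosed stay in the denominator. With *d* = 60%: 0.40 × 0.30 = 12% vs 0.40 × 0.50 = 20%, again 8 points. With no effect (*i* = 20%) and prior disclosure of 50% vs 60%: 10% vs 8%, a spurious −2 points. The wording alone shrinks the bias but removes neither problem.

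**The case against.** **A valid comparison remains.** The same disclosure topic is collected in every arm, and arms were randomised by facility. A reader might infer that all earlier disclosure is credited to the arm, or that the objective cannot be answered. The documents support neither. Earlier disclosure common to both arms cancels when there is no effect (step 3, first row), and disclosure by follow-up can still be compared between arms. What is lost is sensitivity and any means of adjustment.

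**Reversal of sign is unlikely by chance.** A reader might also infer that the result could easily point the wrong way. At 30% vs 50% new disclosure, prior rates of 70% (optimized care) and 50% (self-testing) would give 79% vs 75%. That is a 20-point imbalance. At *d* = 60% the SE is √(0.48 × 1.476 / 600) = 3.4 points, so it lies about 5.8 SE out. The sign flips at about 13 points, or 3.9 SE; at ICC 0.05 that is about 1.8 SE, roughly a 4% one-sided chance.

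Chance is not the only source, however. Enrolment follows an unblinded allocation. Section 3.3.2 has a random subset surveyed in the comparator arms but provider identification and referral in the self-testing arm, while 3.4.4.1 says a random sample. Consent content also differs by arm. Imbalance is therefore a fair worry, though its size is unknown.

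**The forms may be better than the summary.** The protocol summarises survey topics, and the disclosure item sits beside slip and kit distribution, which happen after enrolment. A since-enrolment question is plausible. This stands as a limit on what can be claimed, but step 5 shows it would not be enough.

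**Asking may change behaviour.** Section 3.3.2 withholds detail on partner testing from the comparator arms to avoid influencing clients. A baseline disclosure question could prompt disclosure there. This stands as a cost of the remedy.

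**Conclusion.** The point holds as a design weakness in one secondary objective. As the protocol is written, earlier and new disclosure cannot be separated in any arm. Under equal prior disclosure the observed difference is the true one times (1 − *d*): 8 points instead of 20 at *d* = 60%. Under unequal prior disclosure, a 10-point gap alone yields about 8 spurious points when 20% of the rest disclose.

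All disclosure rates are assumed. The power and imbalance figures also rest on 600 clients per arm and the stated ICC unless marked otherwise. The primary outcome, partner testing, is not affected.

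**What to change.** 1. Add one item per eligible partner to the baseline survey, identical in all three arms: does this partner already know your HIV status?
2. Word the follow-up disclosure item as since enrolment, partner by partner.
3. Define the outcome as new disclosure by follow-up among index client-partner pairs not disclosed at baseline.
4. Report baseline disclosure by arm.
5. Name the outcome in section 3.5.1.1, with an analysis that accounts for clustering by facility and for several partners per client.

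**Cost.** One question per partner on an existing form, and a few lines of protocol text. The denominator shrinks, although in the illustration power still rises. There is some risk of prompting disclosure in comparator clients, which neutral, identical wording placed among the demographic items would limit. A partner-level study code must link baseline to follow-up. That has to be reconciled with sections 3.3.1 and 3.3.2, which describe the comparator surveys as anonymous, whereas the procedures sections have the same clients seen again and traced if late.

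The change makes an imbalance visible and removes old disclosures from the outcome. It does not cure selective recruitment, so the conflicting recruitment descriptions for the self-testing arm should also be reconciled.

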3.3.1. Description of Randomization and Study Arms

Randomization from Aim 1 will be accomplished such that facilities randomized to the self-test intervention in Aim 1 will be self-test intervention sites for Aim 2 and sites randomized to standard of care and optimized standard of care for Aim 1 will continue as standard of care and optimized standard of care sites for Aim 2.

Description of Study Arms

1. **Standard of care arm:** Facilities randomized to the standard of care arm will use MOH approved referral mechanisms, without any intervention from the study team. Standard of care quality will vary by facility and may include some level of partner referral services for index partners such as referral slips. Referral slips may be given at HIV testing or ART clinics. Sites will be asked to counsel clients to have their partners bring referral slips back to the clinic to document the number of partners presenting for HIV testing. A random subset of HIV-positive clients in the standard of care arm will complete an anonymous survey to answer questions about whether they used referral slips and whether they know if partners came to a health facility for testing.

2. **Optimized standard of care arm:** Facilities randomized to optimized standard of care will be supported by the study team to systematically perform referral services following Ministry of Health Guidelines. Providers will receive an initial refresher training on partner testing followed by regular mentoring visits. Job aids will also be used to remind providers about the importance of partner testing. Standard of care procedures involve counseling HIV-positive individuals about the importance of partner testing and providing ‘referral slips’ to the index client to distribute to every sexual partner within the prior 12 months. Referral slips will be used to encourage partners to come to the facility for HIV testing. Sites will be asked to counsel clients to have their partners bring referral slips back to the clinic to document the number of partners presenting for HIV testing. A random subset of participants in the optimized standard of care arm will complete an anonymous survey to answer questions about whether they used referral slips and whether they know if partners came to a health facility for testing.

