3. **Partner self-testing arm:** Facilities randomized to partner self-testing will have study staff give self-test kits to index clients to distribute to every sexual partner with unknown status who lives in the facility catchment area within the prior 12 months (up to three sexual partners). They will also be given self-test kits for themselves so they can participate in couples testing if they choose. All index clients will be counseled on the importance of partner notification and testing and receive a demonstration on how to perform the self-test, so they can show partners. Self-test kits will contain information on how to use the test and a referral card. The referral card will contain information on where to present for confirmatory testing and where partners can receive ART, including a map to the facility. Index clients will be counseled to tell their partner to drop the completed test in a lockbox at the local health facility. A study phone number will also be provided in order to facilitate community-based collection of kits if participants are unwilling or unable to attend the facility. Written instructions, picture instructions, and maps will also be provided to the index client to give to the index partner. Index clients will also be counseled to encourage partners to present to the facility for routine HDA testing if they are unable or uncomfortable completing the self-test.

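### As described, the Aim 2 follow-up surveys in the standard and optimized arms ask only about violence resulting from self-tests, which those clients do not receive, so the survey cannot record violence after a referral slip.

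*Combined protocol and SAP*

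**What the plan says.** All references are to the Aim 2 part of the combined protocol and SAP.

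- **Who receives kits.** Under 3.3.1, facilities in the partner self-testing arm will "have study staff give self-test kits to index clients to distribute to every sexual partner with unknown status". No kits are described for index clients in the other two arms.
- **What the other arms receive.** For the standard arm, 3.3.1 says that care "may include some level of partner referral services for index partners such as referral slips", and 3.4.1.1 describes slips provided "to the index client to distribute to sex partners". In the optimized arm (4.2.1), clients are counselled and "given a partner notification slip to assist in partner notification and testing referral".
- **The violence item.** For the self-testing arm, 3.4.4.4 has the survey find out "whether any gender-based violence or fear of gender-based violence resulted from use of the self-tests". The follow-up paragraphs for the standard arm (4.1) and the optimized arm (4.2) use the same words: staff will "survey the index client to determine whether any gender-based violence or fear of gender-based violence resulted from use of the self-tests".
- **Other harm capture.** The optimized arm also has in-depth interviews with a random sample of 40 index clients, covering "questions around harm or perceived risk of harm due to distributing the referral slip". The Aim 2 qualitative analysis section puts this sample at 30. No interviews are described for the standard arm.

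**The concern.** A client who was given a slip, or nothing, has no self-test to which violence could be attributed. Answered literally, the item would come back as no, or not applicable, for every client in two of the three arms, whatever happened at home after the slip was handed over.

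Partner violence is the one harm that Aim 2 screens for at entry (3.2.1, 3.2.2, 7.3), and section 6 promises that safety will be assessed and reported throughout the study. What is at stake is safety capture and the reading of the self-testing arm's reports. Without the same question in the other arms, a reader could not tell whether reported violence goes with the kits, with partner notification of any kind, or with background violence. That could mislead either way: kits might look harmful beside an empty column, or a real excess might be dismissed for want of a comparator.

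**Working it through.** **1. Exposure and question side by side**

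| Arm | Given to index client | Violence item in follow-up survey refers to | Interviews on harm |
|---|---|---|---|
| Standard (4.1) | Referral slip, possibly none | Self-tests | None described |
| Optimized (4.2) | Referral slip | Self-tests | 40 (or 30) clients |
| Self-testing (4.3) | Self-test kits | Self-tests | 40 (or 30) clients, plus 40 partners |

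The item fits the exposure only in the last row. In 4.1 and 4.2 an earlier sentence of the same paragraph was adapted to slips (the wording there is "whether they gave referral slips to their partner(s"), so the violence clause was most likely carried over from 3.4.4.4 and missed.

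**2. Is the event picked up elsewhere?** The remaining survey items in 4.1 and 4.2 cover disclosure, slips given, partner testing, result and linkage. The register review covers tests, positivity and ART. Section 6 is one general sentence and names no instrument. Section 7.3 concerns screening at entry. That leaves the optimized-arm interviews.

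**3. How far the interviews go.** The chance that a sample of n includes at least one event is 1 − (1 − p)^n. The documents give no p, so p = 1% is an assumption.

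- n = 40: 1 − 0.99^40 = 33%
- n = 30: 1 − 0.99^30 = 26%
- n = 600: 1 − 0.99^600 = 99.8%

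For p from 0.5% to 5%, the chance with 40 interviews runs from 18% to 87%.

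**4. Events the survey item does not ask about.** The expected count is n × p, with p assumed at 1%, 2% or 5% for any violence or fear by follow-up. The Aim 2 sample size section (3.5.1.1) uses 600 per arm.

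- 600 × 0.01 = 6
- 600 × 0.02 = 12
- 600 × 0.05 = 30

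The Schema gives 2,500 per arm instead, for which the ends of the range are 25 and 125. These counts assume every client is reached at follow-up. They are events of any cause, not events caused by a slip.

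**5. What a common item would deliver.** With 5 clusters of 120 per arm, the design effect is 1 + 119 × ICC. The 95% half-width for a between-arm difference is 2.306 × √(2p(1 − p)/n_eff), where 2.306 is the t quantile on 8 degrees of freedom. The plan's ICC of 0.004 was set for testing coverage, so 0.04 is added as an assumed upper value.

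- ICC 0.004: design effect 1.476, n_eff = 600/1.476 = 406.5. Half-widths are 1.6, 2.3 and 3.5 points at p = 1%, 2% and 5%.
- ICC 0.04: design effect 5.760, n_eff = 600/5.760 = 104.2. Half-widths are 3.2, 4.5 and 7.0 points.

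At 1% and 2% the half-width exceeds the event rate itself, so the comparison would be descriptive and imprecise.

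**The case against.** The strongest reply is that this is a drafting slip in prose that describes the survey, not the questionnaire. The questionnaire and the site procedures mentioned in 8.2 are not in the documents, the neighbouring items were adapted to slips, and the form in use may have been right. This stands as a limit: the documents cannot show what clients were asked. It does not remove the point, because site monitors check compliance with the approved protocol (section 5, Site Monitoring) and the protocol text is wrong for two arms.

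Second, the plan treats harm qualitatively, and both arms of the primary contrast (self-testing against optimized care) have interviews that cover harm. That is correct. A reader might infer that violence after a slip goes wholly unrecorded in Aim 2. The documents do not support that, because the optimized-arm interviews ask about harm from the slip. They are few, are not meant to give a rate, and have no counterpart in the standard arm.

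Third, a reader might infer that, with equal true rates of 2%, the wording alone would produce 12/600 in the self-testing arm against 0/600 in a control arm. That is an upper bound on an assumed rate. The 2% is violence or fear from any cause, whereas the item in 3.4.4.4 counts only what resulted from the self-tests, so 12 would appear only if every event were attributed to the kit. The entry exclusions for recent or feared partner violence may also push the true rate to the low end.

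Finally, no prespecified analysis uses the item. That also stands.

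**Conclusion.** The inconsistency is plain on the text. In 4.1 and 4.2 the only violence item in the follow-up survey refers to a product those clients are not given. Followed as written, the survey records no violence after a referral slip in either control arm and supplies no control figure. On an assumed 1% to 5% of clients with an event, that is about 6 to 30 clients per control arm of 600 whose event the item does not ask about. The rate is an assumption and the count is for scale only.

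The primary and secondary tests are untouched: 3.5.1.1 plans no harm comparison. Nor do the figures promise a sharp between-arm contrast once the item is corrected. The defensible gain is that safety events are recorded in the same way in all three arms. Confidence is medium, because the fielded form may already differ from the text.

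**What to change.** In 4.1, 4.2 and 4.3, use one identical item: any partner violence, or fear of partner violence, since baseline. Follow it with one item on whether the client attributes this to the referral slip, the self-test kit, notification or disclosure, or none of these. The neutral first item gives the same count in every arm; the second keeps the attribution that the present wording seeks.

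Report counts and proportions by arm, descriptively, with a cluster-adjusted interval and no hypothesis test. If the fielded questionnaire already asks a suitable question in the control arms, correct the protocol text to match it.

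The cost is one reworded item and one added item at a follow-up visit already planned in all three arms. No new visits, staff or participants are needed. Merely replacing the self-test wording with referral slips in 4.1 and 4.2 would remove the inconsistency, but would still leave arms with differently worded items.
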